For additional information, please refer to the prescribing information for pembrolizumab ([Keytruda 2019](#)) and the Summary of Data and Guidance to the Investigator section of the duvelisib IB.

Table 10: Recommended Dose Modifications for the Management of Overlapping Toxicities for Duvelisib in Combination with Pembrolizumab

Toxicity	Adverse Reaction Grade	During Treatment with Duvelisib in Combination with Pembrolizumab	
		Dose Modification	Recommended Management
Non-infectious Diarrhea or colitis	Grade 1 diarrhea (up to 3 stools per day over baseline) and responsive to antidiarrheal agents, OR Asymptomatic (Grade 1) colitis	
 • No change in pembrolizumab dose • No change in duvelisib dose 	
 • Initiate supportive therapy with antidiarrheal agents as appropriate • Monitor at least weekly until resolved or Grade 0
	Grade 1 diarrhea (up to 3 stools per day over baseline) and unresponsive to antidiarrheal agents	
 • Withhold duvelisib dose • No change in pembrolizumab dose 	
 • Treat with enteric acting steroids (e.g., budesonide) • Monitor at least weekly until resolved • Resume duvelisib at a reduced dose when event resolves (see Table 11)
	Grade 2 diarrhea or colitis	
 • Withhold pembrolizumab and duvelisib 	
 • Administer corticosteroids (initial dose of 1 to 2 mg/kg/day prednisone or equivalent followed by a taper) • Resume in subjects with complete or partial resolution (Grades 0 to 1) after corticosteroid taper
	Abdominal pain, stool with mucus or blood, change in bowel habits, peritoneal signs OR Severe diarrhea or colitis (Grade 3, > 6 stools per day over baseline)	
 • Withhold pembrolizumab and duvelisib 	
 • For Grade 2/Grade 3 colitis, initiate supportive therapy with enteric acting steroids (e.g., budesonide) or systemic steroids (initial dose of 1 to 2 mg/kg/day prednisone or equivalent followed by a taper) • Monitor at least weekly until resolved • Resume pembrolizumab treatment when event resolves • Resume duvelisib at a reduced dose when event resolves (see Table 11) • For recurrent Grade 3 diarrhea or recurrent colitis of any grade, discontinue pembrolizumab and duvelisib
	Life-threatening	
 • Discontinue pembrolizumab and duvelisib 	

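### Table 10 gives overlapping and inconsistent instructions for Grade 2 colitis during combination treatment, at least when the symptoms listed in its next row are present

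*Combined protocol and SAP*

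**What the plan says.** Protocol Section 6.6.1 names non-infectious diarrhea or colitis as a potential overlapping toxicity of the two drugs and refers sites to Table 10 for its management during combination treatment. Two consecutive rows of that table bear on Grade 2 colitis.

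- The first is labelled "Grade 2 diarrhea or colitis". The label carries no condition about symptoms.
- The entry column of the next row has two alternatives. One is a symptom list (abdominal pain, mucus or blood in the stool, altered bowel habit, peritoneal signs) with no grade attached. The other is "Severe diarrhea or colitis (Grade 3, > 6 stools per day over baseline". Grade 2 is not named in this column, but the management column opens with "For Grade 2/Grade 3 colitis, initiate supportive therapy with enteric acting steroids (e.g., budesonide) or systemic steroids".

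Colitis during the Stage 1 duvelisib lead-in is handled separately, in a block of Table 12 restricted to that week.

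Section 6.6.2 adds that a subject whose duvelisib dose is reduced for toxicity may not go back up. Table 11 has only two levels, 25 mg and 15 mg BID.

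**The concern.** A site managing a Grade 2 colitis can find it in two places and receive different directions on steroids, on when to restart, on the dose at restart and on what to do if it recurs.

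Two subjects with the same event could therefore be handled differently, both within the protocol. Because a duvelisib reduction is one-way, such a difference would persist through the rest of treatment. It would enter the exposure tables (Section 9.4.4), the exposure-response analysis (Section 9.4.6) and the tolerability picture, which is the primary objective of Stage 1.

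**Working it through.** No arithmetic applies, and the plan states no figure on this point. The check sets the two rows side by side and asks three questions.

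| Item | Grade 2 row | Next row | Result |
|---|---|---|---|
| Withholding | Both drugs | Both drugs | Same |
| Steroids | "Administer corticosteroids (initial dose of 1 to 2 mg/kg/day prednisone or equivalent followed by a taper" | Enteric-acting or systemic; the systemic option has the same starting dose and a taper | Differ: the enteric option is in one row only |
| Resuming pembrolizumab | "Resume in subjects with complete or partial resolution (Grades 0 to 1) after corticosteroid taper" | "Resume pembrolizumab treatment when event resolves" | Differ: partial resolution after a taper against resolution |
| Resuming duvelisib | Same sentence; no dose level and no pointer to Table 11 | "Resume duvelisib at a reduced dose when event resolves" | Differ: silence against an explicit reduction |
| Recurrence | No rule | "For recurrent Grade 3 diarrhea or recurrent colitis of any grade, discontinue pembrolizumab and duvelisib" | In one row only |

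**Which events meet both rows?** The Grade 2 row excludes nothing on the basis of symptoms. A Grade 2 colitis with any listed symptom therefore meets its label, and also meets both the entry column and the management text of the next row. Table 10 describes Grade 1 colitis as asymptomatic, which implies that Grade 2 colitis usually has symptoms, so the overlap may be common. A Grade 2 colitis without any listed symptom meets the next row only through its management text. Grade 2 diarrhea without those symptoms is covered only by the Grade 2 row.

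**Does any text give one row priority?** None was found. Sections 6.6.1 and 6.6.2 do not rank the rows. Table 8 sends sites to Tables 10 and 13 for steroid use in managing toxicity, which brings the reader back to the same two rows. The colitis entries in Table 12 are limited to the lead-in.

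**Does the silence on restart dose matter?** Elsewhere Table 10 states a reduced duvelisib dose on restart for Grade 1 diarrhea that does not respond to antidiarrheals, for Grade 3 cutaneous reactions and for Grade 2 pneumonitis. A reader of the Grade 2 row cannot tell whether the omission is deliberate. Under Section 6.6.2 the choice has further effects: there is no re-escalation, 15 mg BID is the lowest level, unacceptable toxicity at that level ends study treatment, and stopping duvelisib also stops pembrolizumab. Different restart criteria can also give different hold lengths against the 42-day limit in Section 6.6.2 (Section 7.1 lets the Medical Monitor approve an exception).

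**The case against.** The best defence has four parts.

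- **Reading the entry column first.** Grade 2 does not appear in the next row's entry column, so on this reading a Grade 2 colitis without the listed symptoms belongs to the Grade 2 row alone. This stands and limits the scope. It does not help a Grade 2 colitis with those symptoms, and it leaves unexplained why the next row's management text names Grade 2.
- **The rows are not mutually exclusive.** Both withhold both drugs, both contain the same systemic steroid option, and full resolution is one of the outcomes the Grade 2 row accepts. Section 6.6.2 also allows the duvelisib dose to be modified for overlapping toxicities, so a reduction is not ruled out under the Grade 2 row. A site could act in a way compatible with both rows. This stands too, but each row also permits conduct that the other does not, and that is where sites can diverge.
- **These are recommendations.** Section 6.6 presents them as general guidance, and Section 6.6.1 asks for discussion with the Medical Monitor when pembrolizumab is suspected. This softens the problem. Guidance that points two ways still needs correcting.
- **Little of the analysis depends on it.** Counts and grades of adverse events at onset are the same whichever row is followed. Delays and reductions are recorded in the CRF (Section 6.4), so divergence would be visible. The general non-hematologic DLT criterion in Section 6.7.1 starts at Grade 3, so a Grade 2 colitis would reach the DLT count only through the permanent-discontinuation or discretionary clause. All of this stands. What remains exposed is dose received, time on treatment and the tolerability summary.

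**Conclusion.** The inconsistency is real and is in the current text. During combination treatment, a non-infectious Grade 2 colitis with the symptoms listed in the next row falls under two sets of instructions. They differ on steroid options, restart threshold and restart dose, and only one has a recurrence rule. The row followed can fix a subject's later duvelisib dose.

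Three stronger inferences are not supported:

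- **That every Grade 2 colitis is affected.** Lead-in events fall under Table 12, and the next row's entry column does not name Grade 2. The overlap is certain only for cases with the listed symptoms.
- **That the two rows prescribe 25 mg against 15 mg, a (25 − 15)/25 = 40% difference.** The Grade 2 row states no dose. The figure needs a subject on 25 mg BID and a site that reads the silence as an unchanged dose. It does not apply to a subject already on 15 mg.
- **That such cases would be a noticeable share of the safety data in 30 subjects.** The documents give no expected frequency of Grade 2 colitis, so the number affected is unknown. Nor do they show any effect on ORR or on the two-stage decision.

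This is a drafting inconsistency in safety instructions. It is worth correcting because it is cheap to remove and its dose consequence cannot be undone for the subject concerned. No view is taken on which instruction is clinically right.

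**What to change.** Reconcile the two rows of Table 10 so that each grade of diarrhea and of colitis has one set of instructions on steroids, resumption of each drug, duvelisib restart dose and recurrence. The entry column and the management text of each row should name the same grades. If symptoms are meant to separate the rows, the entry column should say so. The sponsor's clinical team decides the content.

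The cost is an edit to one table and a notice to sites. A formal amendment would need IRB/IEC approval under Section 10.6.1. The sponsor has already sent a clarification memorandum on a smaller point, the Cycle 5 PK draw, so a way of alerting sites exists. Sample size, endpoints and analyses do not change.

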 - Total bilirubin level $\leq 1.5 \times$ ULN (exception: subjects with Gilbert's Syndrome may have a bilirubin level $> 1.5 \times$ ULN)
 - AST/serum glutamic-oxaloacetic transaminase (SGOT) and ALT/serum pyruvic transaminase (SGPT) levels $\leq 2.5 \times$ ULN or $\leq 5 \times$ ULN in subjects with liver metastases
- 10. Must have international ratio (INR) or prothrombin time (PT) and activated partial thromboplastin time (aPTT) $\leq 1.5 \times$ ULN, unless subject is receiving anticoagulant therapy in which case PT or aPTT must be within therapeutic range of intended use of anticoagulants
- 11. Must have an Eastern Cooperative Oncology Group (ECOG) performance status ≤ 1
- 12. For male and female subjects of reproductive potential (i.e., not surgically sterile or female subjects who are not postmenopausal), must be willing to use a highly effective method of contraception (see Section 10.4) for the duration of the study interventions and for at least 4 months after the last dose of study interventions
- 13. Must have a negative serum human chorionic gonadotropin (hCG) pregnancy test result within 7 days before first dose of duvelisib if the subject is a woman of childbearing potential (WCBP) (defined in Section 10.4)
- 14. Must provide signed and dated institutional review board (IRB)/independent ethics committee (IEC)-approved informed consent form (ICF) before any study-specific screening procedures are performed

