Toxicity	Adverse Reaction Grade	During Treatment with Duvelisib in Combination with Pembrolizumab	
		Dose Modification	Recommended Management
Cutaneous reactions	Grade 1-2	
 No change in dose for pembrolizumab or duvelisib 	
 Initiate supportive care with emollients, anti-histamines (for pruritus), or topical steroids Monitor closely
	Grade 3	
 Withhold duvelisib dose Based on the severity of the adverse reaction, withhold or permanently discontinue pembrolizumab 	
 Initiate supportive care with emollients, antihistamines (for pruritus), or topical steroids Monitor at least weekly until resolved Resume duvelisib at reduced dose when event resolves (see Table 11) If severe cutaneous reaction does not improve, worsens, or recurs, discontinue duvelisib
	Life-threatening	
 Discontinue pembrolizumab and duvelisib 	
	SJS, TEN, DRESS (any grade)	
 Discontinue pembrolizumab and duvelisib 	
Pneumonitis without suspected infectious cause	Moderate (Grade 2) symptomatic pneumonitis	
 Withhold pembrolizumab and duvelisib 	
 Treat with corticosteroids (1 to 2 mg/kg/day prednisone or equivalent, followed by corticosteroid taper) If pneumonitis recovers to Grade 0 or 1, pembrolizumab may be resumed and duvelisib may be resumed at reduced dose (see Table 11) If non-infectious pneumonitis recurs or subject does not respond to steroid therapy, discontinue duvelisib and pembrolizumab
	Recurrent Grade 2 pneumonitis, severe (Grade 3), or life-threatening pneumonitis	
 Discontinue pembrolizumab and duvelisib 	

Toxicity	Adverse Reaction Grade	During Treatment with Duvelisib in Combination with Pembrolizumab	
		Dose Modification	Recommended Management
Hepatotoxicity	AST or ALT > 3 and up to 5 × ULN or total bilirubin > 1.5 and up to 3 × the ULN	
 Withhold pembrolizumab and duvelisib 	
 Treat with corticosteroids (0.5 to 1 mg/kg/day prednisone or equivalent followed by corticosteroid taper) Monitor at least weekly until ALT or AST returns to < 3 × ULN Resume treatment when adverse reaction improves to Grade 0 or 1 after corticosteroid taper

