	In subjects without liver metastases, AST or ALT > 5 × ULN or total bilirubin > 3 × ULN	
 Discontinue pembrolizumab and duvelisib 	
	In subjects with liver metastasis and Grade 2 AST or ALT at baseline, with an increase in AST or ALT of 50% or more relative to baseline that persists for at least 1 week	
 Discontinue pembrolizumab and duvelisib 	

Abbreviations: ALT: alanine aminotransferase; AST: aspartate transaminase; DRESS: drug reaction with eosinophilia and systemic symptoms; SJS: Stevens Johnson syndrome; TEN: toxic epidermal necrolysis; ULN: upper limit of normal.

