	Abdominal pain, stool with mucus or blood, change in bowel habits, peritoneal signs, OR Severe diarrhea (Grade 3, > 6 stools per day over baseline)	
 • Withhold duvelisib until resolved • Initiate supportive therapy with enteric acting steroids (e.g., budesonide) or systemic steroids • Monitor at least weekly until resolved • Resume at a reduced dose (see Table 11) • For recurrent Grade 3 diarrhea or recurrent colitis of any grade, discontinue duvelisib
	Life-threatening	
 • Discontinue duvelisib
Cutaneous reactions	Grade 1-2	
 • No change in dose • Initiate supportive care with emollients, anti-histamines (for pruritus), or topical steroids • Monitor closely
	Grade 3	
 • Withhold duvelisib until resolved • Initiate supportive care with emollients, anti-histamines (for pruritus), or topical steroids • Monitor at least weekly until resolved • Resume at a reduced dose (see Table 11) • If severe cutaneous reaction does not improve, worsens, or recurs, discontinue duvelisib
	Life-threatening	
 • Discontinue duvelisib
	SJS, TEN, DRESS (any grade)	
 • Discontinue duvelisib
Pneumonitis without suspected infectious cause	Moderate (Grade 2) symptomatic pneumonitis	
 • Withhold duvelisib • Treat with systemic steroid therapy • If pneumonitis recovers to Grade 0 or 1, duvelisib may be resumed at reduced dose (see Table 11) • If non-infectious pneumonitis recurs or subject does not respond to steroid therapy, discontinue duvelisib
	Severe (Grade 3) or life-threatening pneumonitis	
 • Discontinue duvelisib • Treat with systemic steroid therapy

Toxicity	Adverse Reaction Grade	Dose Modification and Recommended Management
ALT/AST elevation	3 to 5 × ULN (Grade 2)	
 Maintain duvelisib dose Monitor at least weekly until return to < 3 × ULN
	> 5 to 20 × ULN (Grade 3)	
 Withhold duvelisib and monitor at least weekly until return to < 3 × ULN Resume duvelisib at same dose (first occurrence) or at a reduced dose for subsequent occurrence (see Table 11)
	> 20 × ULN (Grade 4)	
 Discontinue duvelisib

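### Table 10 names no action for subjects with liver metastases whose AST/ALT rises above 5 × ULN from a baseline below Grade 2, or whose bilirubin exceeds 3 × ULN

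*Combined protocol and SAP*

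**What the plan says.** Inclusion criterion 9c (Section 5.1) allows AST and ALT up to 2.5 × ULN, raised to 5 × "ULN in subjects with liver metastases". It caps bilirubin at 1.5 × ULN, with an "exception: subjects with Gilbert's Syndrome may have a bilirubin level" above that.

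For combination treatment, the hepatotoxicity part of Table 10 (Section 6.6.1) has three rows:

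- **Hold row.** For "AST or ALT > 3 and up to 5 × ULN or total bilirubin > 1.5 and up to 3 × the ULN", withhold both drugs, give prednisone 0.5 to 1 mg/kg/day with a taper, and then "Resume treatment when adverse reaction improves to Grade 0 or 1 after corticosteroid taper".
- **General discontinuation row.** "In subjects without liver metastases, AST or ALT > 5 × ULN or total bilirubin > 3 × ULN": discontinue both drugs.
- **Liver-metastasis row.** This row opens "In subjects with liver metastasis and Grade 2 AST or ALT at baseline". It then asks for values at least half as high again as at entry, sustained for a week or longer, and discontinues both drugs.

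Table 12 (Section 6.6.2) equates Grade 2 ALT/AST with 3 to 5 × ULN. Its own ALT/AST rows apply only to the duvelisib lead-in, and its footnote a sends the reader to Table 10 for the combination. Table 13 (Section 6.6.3) covers pembrolizumab's non-overlapping toxicities and has no hepatitis row.

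**The concern.** The general discontinuation row excludes everyone with liver metastases, and the row written for them takes back only those whose AST or ALT was already Grade 2 at entry. A subject with liver metastases and normal enzymes at entry falls between the two. The liver-metastasis row does not mention bilirubin, so bilirubin above 3 × ULN has no row in any subject with liver metastases.

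The stopping guidance is then inverted: the larger rise from the better baseline has no stated action, and the smaller rise from the worse baseline stops treatment. Section 2.4 calls this the first clinical study of duvelisib with a PD-1 inhibitor, Sections 2.4.1 and 6.6.1 name ALT/AST elevation as a potential overlapping toxicity, and Section 9.6 provides no data monitoring committee. Sites depend on this table.

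A lesser concern is the hold row. It uses fixed multiples of ULN with no reference to baseline, so some values admitted by criterion 9c meet it with no change at all. That conflicts with the liver-metastasis row, which presupposes that subjects with a Grade 2 baseline are on treatment and judged against their own starting value.

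**Working it through.** The plan gives no figure to reproduce; the check is whether the rows cover the possible cases. Let *b* be baseline AST or ALT and *x* the current value, both in × ULN, taking one analyte at a time. (A second abnormal test could bring the subject into a row by itself.)

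Rules as written:

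- Hold: 3 < *x* ≤ 5, or bilirubin > 1.5 to 3.
- General discontinuation: no liver metastases, and *x* > 5 or bilirubin > 3.
- Liver-metastasis discontinuation: liver metastases, 3 ≤ *b* ≤ 5 (Grade 2 per Table 12), *x* ≥ 1.5 × *b*, lasting at least 1 week.

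| Liver metastases | *b* | *x* | *x*/*b* | Row met |
|---|---|---|---|---|
| No | 1 | 6 | 6.0 | Discontinue |
| Yes | 1 | 10 | 10.0 | None |
| Yes | 1 | 25 | 25.0 | None |
| Yes | 2.5 | 6 | 2.4 | None |
| Yes | 4 | 6 for ≥ 1 week | 1.5 | Discontinue |
| Yes | 4 | 5.5 | 1.38 | None |
| Yes | 4 | 4 | 1.0 | Hold |
| Yes | 3.2 | 4.9 for ≥ 1 week | 1.53 | Hold and discontinue |

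**Baseline below Grade 2, liver metastases.** The uncovered region is every *x* > 5, with no upper end. It starts at a fold rise of 5/*b*: 5/1 = 5.0, 5/2 = 2.5, 5/2.5 = 2.0, and 5/3 = 1.67 for a baseline just under 3.

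**Bilirubin above 3 × ULN, liver metastases.** The hold row ends at 3, the general row excludes these subjects, and the liver-metastasis row concerns AST and ALT only. No row is met.

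**Grade 2 baseline.** The discontinuation threshold is 1.5 × *b*: 4.5 for *b* = 3, 6.0 for 4, 7.5 for 5. It passes 5 × ULN at *b* = 5/1.5 = 3.33. Above that baseline, values between 5 and 1.5 × *b* meet no row (5 to 6 for *b* = 4; 5 to 7.5 for *b* = 5). For baselines just above 3 up to 3.33, a sustained 50% rise can still lie at or below 5, so the hold and discontinuation rows both apply.

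**Hold row at a 0% rise.** It is met by entry AST/ALT > 3 to 5 × ULN with liver metastases, and by entry bilirubin > 1.5 to 3 × ULN in Gilbert's Syndrome. Criterion 9c admits both.

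**Other places that might fill the gap.**

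- Table 12's ALT/AST rows end with the lead-in, which Stage 2 subjects do not have.
- Table 13 has a general row for other immune-mediated reactions, but Section 6.6.3 limits that table to non-overlapping toxicities, and it directs pembrolizumab only.
- The DLT definition (Section 6.7.1) counts Grade 3 ALT/AST lasting over 1 week and any Grade 4, but only in Cycle 1 of Stage 1, with DLTs assessed in the first 6 subjects.

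**The case against.** The strongest reply is that Table 10 is headed as recommended guidance and is not the only safeguard. Section 7.1 lets the Investigator stop for unacceptable toxicity, Section 8 sends urgent safety concerns to the Sponsor at once, Section 6.6.2 allows duvelisib to be held for toxicity, and Section 6.6.1 refers to the pembrolizumab label and the duvelisib Investigator's Brochure. A reader might infer from the gap that a subject at 10 × ULN would simply stay on both drugs. The documents do not support that: an investigator who holds at 4 × ULN is unlikely to continue at 10. What stands is that the table written to direct the decision does not direct it for these subjects, and the outside sources cannot be checked here.

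On the hold row the reply is stronger. A reader might infer that the protocol obliges sites to interrupt treatment and give steroids for stable entry values. It does not. The rows concern adverse reactions; Section 8.4.1 leaves out pre-existing conditions without clinically significant worsening; Sections 8.2.4 and 8.4.6 leave the significance of a disease-related laboratory value to the Investigator. Two further inferences also fail:

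- That resumption requires a value below the subject's own baseline. This depends on how CTCAE 5.0 grades an abnormal baseline, and that text is not reproduced.
- That a long hold forces permanent discontinuation. The 42-day limit in Section 6.6.2 applies to treatment-related toxicity, and Section 7.1 lets the Medical Monitor approve a longer interruption.

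A reader might also count the band above 5 × ULN for Grade 2 baselines as the same defect. No row is met there, but not discontinuing below a 50% rise is the evident purpose of that threshold.

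Finally, Table 25 says the Version 2.0 liver rules were meant to align with prescribing information and to be the more conservative choice, because immune-related elevations are hard to tell from others. That supports strict thresholds. It explains neither a missing row for a new, larger rise nor a hold for a value unchanged since entry.

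**Conclusion.** The main point holds on the text. During combination treatment, Table 10 names no action for a subject with liver metastases when AST/ALT exceeds 5 × ULN from a baseline below Grade 2, or when bilirubin exceeds 3 × ULN. No other dose-modification table covers these cases, and the DLT definition reaches only Cycle 1 of Stage 1. The table should be changed, because a stopping rule that misses the larger rise is a patient-safety defect with a short repair.

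The hold row's missing baseline clause is a secondary point of lower severity. It invites different handling between sites, but the adverse-event definitions give investigators a way round it.

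The conclusion assumes a literal reading of the rows and Table 12's range for Grade 2. The number of subjects affected is unknown, since the documents give no frequency of liver metastases or Gilbert's Syndrome among the 30 planned. A reader might look for a consequence for the efficacy result; none is claimed for power, sample size or the ORR test.

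**What to change.** 1. Reword the general discontinuation row so that AST/ALT > 5 × ULN applies to all subjects except those with liver metastases and Grade 2 baseline AST/ALT, who keep the 50%-for-1-week rule. Let bilirubin > 3 × ULN also cover subjects with liver metastases. The cases 1 to 10 and 2.5 to 6 × ULN then lead to discontinuation. A fixed 5 × ULN limit should not be imposed on Grade 2 baselines: it would catch 4.9 to 5.1 × ULN, a 4% rise (0.2/4.9).
2. Add to the hold row that, for subjects with liver metastases and Grade 2 baseline AST/ALT, or with Gilbert's Syndrome, it applies only to a clinically significant worsening from baseline, with resumption at baseline or Grade 0 to 1.
3. As an editorial correction, add Table 10 to note 1 of Table 23 (Section 10.3), which sends readers to Tables 12 and 13 for liver stopping criteria.

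The clinical team should confirm the thresholds. The cost is one reworded row, one sentence and one cross-reference. The downside is slightly fewer holds in a small subgroup of unknown size, and added discontinuations for subjects with liver metastases in the cells now uncovered. Eligibility and the planned analyses do not change.
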